5.9 Peripheral Blood Stem Cell Mobilization and Collection

Peripheral blood stem cells may be mobilized during study treatment at the discretion of the investigator.

Collection of PBSC for ASCT, if applicable, should occur per institutional standard of care. If initial stem cell collection is inadequate, additional collection of peripheral blood stem cells for ASCT may be performed per institutional standards.

5.10 Treatment Compliance

Study drug administration will be performed by study site staff and documented in source documents and the CRF.

6 STUDY ACTIVITIES

6.1 Schedule of Events

Adverse events (AEs) and concomitant medications will be recorded from Day 1 (predose) through the safety reporting period (see Section 7.7.1.3). Any study protocol-related AE should be recorded from the time of informed consent as well as any concomitant medications given for the treatment of the AE.

Beyond the safety reporting period, patients may undergo subsequent ASCT. Additional transplant-related data will be collected following ASCT and may include, but not be limited to, the time to neutrophil and platelet engraftment in each treatment arm.

A schedule of events is provided in [Appendix A](#). Study activities are listed by visit in this section, and descriptions of all study assessments are presented in Section 7.

6.2 Screening Visit (Day –28 to Day 1)

- Informed consent
- Study eligibility per inclusion/exclusion criteria (see Section 4)
- Medical history; medical history at screening includes a review of inflammatory conditions (see Section 7.1)
- Collection/acquisition of tumor specimen for central pathology review (see Section 7.1)
- Patient second-line, age-adjusted International Prognostic Index (saaIPI) score for patients ≤ 60 years of age or standard IPI score for patients > 60 years of age (see [Appendix D](#))
- Serology for hepatitis B surface antigen and anti-hepatitis B core antibody; if either is positive, PCR for hepatitis B viremia must also be performed (see Section 5.5.1)
- Blood sample for biomarker assessments ([Table 3](#))
- CT of diagnostic quality of neck, chest, abdomen, and pelvis (see Section 7.2)
- PET scan (Note: a combined CT/PET may be obtained to satisfy the requirements for CT and PET scanning, as long as the CT is of diagnostic quality)

- If a bone marrow biopsy has been performed as part of standard of care, record the biopsy result for lymphoma involvement in the CRF (see Section 7.2; a result from a biopsy collected within 60 days prior to the first dose of study treatment may be used)
- Ophthalmology exam (see Section 7.7.5)
 - Ocular health survey (± 2 days from the ophthalmology exam)

6.2.1 Baseline Visit (Day –7 to Day 1)

- Physical exam (see Section 7.7.4)
- Height and weight
- B symptom assessment (see Section 7.2)
- ECOG performance status (see Appendix B)
- Electrocardiogram (ECG)
- Pregnancy test for females of childbearing potential
- Serum chemistry panel, including fasting blood glucose (see Section 7.7.3)
- Hemoglobin A1c (Hgb A1c)
- Complete blood count (CBC) with differential (see Section 7.7.3)
- Prothrombin time, partial thromboplastin time, international normalized ratio (PT/PTT/INR)
- Spot urine for urine protein:creatinine (UPC) ratio (see Section 7.7.3)

6.3 Randomization (Day –1 to Day 1)

Randomization to occur after eligibility is determined and within 1 business day prior to the planned first dose of Cycle 1 Day 1.

- For the 19A+RICE Arm: Begin prophylactic steroid eye drop administration. Steroid eye drop prophylaxis is recommended to begin 1 day prior to denintuzumab mafodotin dose if possible (see Section 5.4.1); however, beginning steroid eye drop prophylaxis on Day 1 for the first cycle of treatment is acceptable.

6.4 Treatment Period (Day 1 to Day 21)

6.4.1 Cycle 1, Day 1

All Day 1 assessments should be completed prior to study drug administration.

- Vital signs (see Section 7.7.2)
- Serum chemistry panel
- CBC with differential
- PT/PTT/INR
- Spot urine for UPC ratio
- Blood samples for PK, ATA, and biomarker assessments (see Table 3)
- For the 19A+RICE Arm:
 - Denintuzumab mafodotin administration

- Prophylactic steroid eye drop administration starting 1 day before infusion, if not already started
- Recommended prophylactic ocular interventions at the time of infusion: cooling eye mask application and vasoconstrictor eye drops administration (see [Table 1](#))

If Baseline Visit activities occur within 1 day prior to Cycle 1, Day 1, the following assessments do not need to be repeated at the Cycle 1 Day 1 visit: serum chemistry panel, CBC with differential, PT/PTT/INR, and spot urine for UPC calculation.

6.4.2 Cycle 1, Day 1 to Day 3 (+1 day)

- RICE administration (see Section [5.3.3](#))
- Days 1 and 2: Blood samples for PK, ATA, and biomarker assessments (see [Table 3](#))

6.4.3 Cycle 1, Day 4

- Blood samples for PK and biomarker assessments (see [Table 3](#))

6.4.4 Cycle 1, Day 8 (±1 day)

- Serum chemistry panel
- CBC with differential
- Spot urine for UPC ratio
 - 24-hour urine collection if UPC >2 (prior to next cycle dosing, or prior to EOT visit if discontinuing study treatment)
- Blood samples for PK and biomarker assessments (see [Table 3](#))

6.4.5 Cycle 1, Day 15 (±1 day)

- Serum chemistry panel
- CBC with differential
- Spot urine for UPC ratio
 - 24-hour urine collection if UPC >2 (prior to next cycle dosing, or prior to EOT visit if discontinuing study treatment)
- Blood samples for PK and biomarker assessments (see [Table 3](#))

6.4.6 Cycle 1, Day 22 (±3 days)

For patients who do not continue on treatment or do not start the next cycle on Day 22 due to dose delay:

- Blood sample for PK (see [Table 3](#))

6.4.7 Cycles 2 and 3: Day 1 (±1 day)

- Perform the following procedures within 24 hours prior to administration of the first component of study treatment
 - Physical exam, including weight

- Vital signs (see Section 7.7.2)
- ECOG performance status
- B symptom assessment
- Serum chemistry panel
- CBC with differential
- PT/PTT/INR
- Spot urine for UPC ratio
 - 24-hour urine collection if UPC >2 (prior to next cycle dosing, or prior to EOT visit if discontinuing study treatment)
- Blood samples for PK, ATA, and biomarker assessments (see Table 3)
- For the 19A+RICE Arm:
 - Denintuzumab mafodotin administration
 - Prophylactic steroid eye drop administration. Note: Eye drop prophylaxis should begin 1 day prior to denintuzumab mafodotin dose (see Section 5.4.1).
 - Recommended prophylactic ocular interventions at the time of infusion: cooling eye mask application and vasoconstrictor eye drops administration (see Table 1)

6.4.8 Cycles 2 and 3: Day 1 to Day 3 (±1 day)

- RICE administration

6.4.9 Cycles 2 and 3: Day 8 (±1 day)

- Serum chemistry panel
- CBC with differential
- Spot urine for UPC ratio
 - 24-hour urine collection if UPC >2 (prior to next cycle dosing, or prior to EOT visit if discontinuing study treatment)

6.4.10 Cycles 2 and 3: Day 15 (±1 day)

- Serum chemistry panel
- CBC with differential
- Spot urine for UPC ratio
 - 24-hour urine collection if UPC >2 (prior to next cycle dosing, or prior to EOT visit if discontinuing study treatment)
- Ophthalmology exam (performed Day 14 to Day 21 of the treatment cycle, unless alternate schedule is approved by the medical monitor; see Section 7.7.5). Review exam results prior to next dosing of denintuzumab mafodotin; dose modifications should be made based on ocular toxicity grading (see Table 2 and Appendix E).
 - Ocular health survey (±2 days from the ophthalmology exam)

6.4.11 Cycle 2, Day 22 (± 3 days)

For patients who do not continue on treatment or do not start the next cycle on Day 22 due to dose delay:

- Blood sample for PK (see [Table 3](#))

6.5 PBSC Mobilization

PBSC mobilization for ASCT should occur per institutional standard of care. Chemotherapy for the mobilization of stem cells is permitted. Information surrounding PBSC mobilization and collection, if conducted, will be collected and may include, but not be limited to, the following: date of mobilization, number of CD34-positive cells mobilized (cells/kg), and mobilization regimen.

6.6 End of Treatment Visit

End of Treatment (EOT) visits should occur 14 to 30 days after the start of the last cycle (administration of denintuzumab mafodotin in the 19A+RICE Arm, or Day 1 of RICE in the control arm), unless delayed due to an AE. However, EOT evaluations must be performed before initiation of a new therapy, inclusive of radiotherapy and ASCT. If EOT evaluations are completed before 30 days after completion of study treatment, the patient will also be contacted 30–37 days following the completion of study treatment to assess for adverse events.

- Physical examination
- Review of inflammatory conditions (only for those patients with certain inflammatory conditions of interest at Screening/Baseline)
- ECOG performance status
- B symptom assessment
- ECG
- Ophthalmology exam (not required if an exam was performed within 4 weeks prior to the EOT visit, and following the last dose of study treatment)
 - Ocular health survey (± 2 days from the ophthalmology exam)
- Pregnancy test for females of childbearing potential
- Serum chemistry panel
- CBC with differential
- PT/PTT/INR
- Spot urine for UPC calculation
 - 24-hour urine collection if UPC > 2 (within 5 days after UPC assessment)
- Blood samples for PK, ATA, and biomarker assessments (see [Table 3](#))
- For patients discontinuing treatment due to disease progression: if a tumor biopsy was performed at the time of disease progression as part of standard of care, submit sample of tumor specimen, if available (see [Section 7.4.4](#))

The following response assessments are required (unless progressive disease [PD] was documented within the previous 6 weeks by diagnostic CT/PET scan):

- CT of diagnostic quality of neck, chest, abdomen, and pelvis (see Section 7.2)
- PET scan (Note: a combined CT/PET may be obtained to satisfy the requirements for CT and PET scanning, as long as the CT is of diagnostic quality)
- If patient is scheduled to undergo stem cell collection and bone marrow biopsy is performed as part of standard of care, record the bone marrow biopsy result for lymphoma involvement in the CRF.

6.7 Long-Term Follow-Up Visits

Patients who discontinue from study treatment will remain on the study for follow-up until discontinuation from the study by withdrawal of consent, loss to follow-up, death, or study closure, whichever occurs first (see Section 4.3.2).

For patients who discontinue study treatment for any reason other than disease progression or initiation of a non-protocol therapy (with the exception of ASCT) for treatment of lymphoma, long-term follow-up visits for PFS assessment will occur at 3, 6, 12, 18, 24 months (± 1 month), and then annually after ASCT or EOT (for patients who don't receive ASCT).

The following assessments will be performed at long-term follow-up visits:

- Clinical assessment of disease status by history and physical examination
- CT scan of diagnostic quality of the neck, chest, abdomen, and pelvis (see Section 7.2) until disease progression or initiation of a new anticancer treatment (with the exception of a stem cell transplant); perform at follow-up visits and at any time disease progression is suspected
- PET scan, unless disease is PET negative; required until disease is PET negative (Note: a combined CT/PET may be obtained to satisfy the requirements for CT and PET scanning, as long as the CT is of diagnostic quality)
- Record subsequent anticancer therapies received
- For patients who receive ASCT, collect PBSC mobilization outcomes, and time to neutrophil and platelet engraftment

At any time during the follow-up period, if a bone marrow biopsy is performed as part of standard of care, the results from the bone marrow biopsy for lymphoma involvement will be recorded in the CRF.

For patients who proceed to ASCT, an ophthalmology exam and ocular health survey will be performed approximately 30-days post ASCT.

In addition, for patients who develop ocular toxicity during study treatment, ophthalmologic exams should be conducted monthly during the follow-up period (unless discussed with the medical monitor) until resolution or return to baseline.

All patients who receive at least one dose of denintuzumab mafodotin in the experimental arm or RICE in the control arm will be followed for survival at 6-month intervals after ASCT or EOT for the first 24 months and then yearly thereafter until death or study closure, whichever occurs first. At the time of study closure, patients will be contacted for a final survival assessment.

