PET scans and computed tomography (CT) scans of the neck, chest, abdomen, and pelvis, will be assessed at baseline and at end of treatment (EOT). CT scans will be of diagnostic quality (i.e., contrast-enhanced with IV and oral contrast, unless contrast is medically contraindicated). Follow-up assessments will be performed at 3, 6, 12, 18, 24 months, and then annually after ASCT or EOT (for patients who don't receive ASCT). For all follow-up assessments, both PET and CT scans are required until disease is PET negative; responses will then be followed by CT scans of diagnostic quality. Follow-up assessments will continue until disease progression, initiation of a new anticancer treatment (with the exception of a stem cell transplant), or study closure, whichever occurs first.

At screening and/or at any time on study, if a bone marrow biopsy is performed as part of standard of care, the results from the biopsy report for the presence of lymphoma will be recorded in the case report form (CRF). A CT scan of diagnostic quality will be performed at the time of suspected clinical progression. Survival status follow-up will continue until patient death or study closure, whichever occurs first.

Subsequent ASCT is permitted, based on investigator discretion and standard of care, and is recommended to occur within 8 weeks of Cycle 3 Day 1 (Philip 1995). Data will be recorded to assess adequacy of hematopoietic stem cell collection and transplant.

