9.2.2 Secondary Efficacy Endpoints

9.2.2.1 Progression-Free Survival (PFS)

PFS is defined as the time from randomization to first documentation of disease progression per investigator (including progressive metabolic disease by PET/CT or progressive disease by CT as assessed by the Lugano classification criteria ([Cheson 2014](#)), or investigator claim of clinical progression), death due to any cause, or receipt of subsequent anticancer therapy, whichever comes first. Note that patients receiving post-treatment consolidative radiotherapy, post-treatment chemotherapy for the purpose of mobilizing PBSC, or ASCT will not be considered as having started new anticancer therapy.

PFS by IRF may also be evaluated.

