3. Stratified log-rank test by stratification factors recorded on the baseline disease diagnosis CRF will be used to compare the PFS by investigator between the treatment groups. PFS will be censored according to Table 1.
4. Allogeneic SCT will not be regarded as an event.

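### Scheduled follow-up imaging stops at any new anticancer treatment except stem cell transplant, but PFS and duration of response also exempt consolidative radiotherapy and mobilising chemotherapy, so some patients still at risk have no required scheduled scans

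*Protocol*

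**What the plan says.** **Conduct text.** Protocol 6.7 requires diagnostic CT at follow-up visits "until disease progression or initiation of a new anticancer treatment (with the exception of a stem cell transplant". Section 3.1 applies the same limit to follow-up assessments generally: "Follow-up assessments will continue until disease progression, initiation of a new anticancer treatment (with the exception of a stem cell transplant), or study closure". The synopsis and the Figure 1 footnote repeat it. Each names one exception, a stem cell transplant.

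**Endpoint text.** The PFS definition in 9.2.2.1 has a longer list: "Note that patients receiving post-treatment consolidative radiotherapy, post-treatment chemotherapy for the purpose of mobilizing PBSC, or ASCT will not be considered as having started" a new anticancer therapy. Sections 9.2.2.3 (duration of CR) and 9.2.2.7 (duration of objective response) use the same three exemptions, as do SAP 7.5.2.1, 7.5.2.2 and 7.5.2.5.

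**Assessment and censoring.** SAP 6.4 accepts a physical examination during long-term follow-up as adequate evidence that a responder has not progressed by investigator assessment. SAP 7.5.2.1 says that patients who start consolidative radiotherapy or a mobilising regimen before progression or new therapy are censored at the last disease assessment without progression, and it counts a follow-up physical examination as such an assessment.

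**Testing.** PFS and then duration of CR, both per investigator, follow CR rate in a fixed sequence at two-sided alpha 0.1 (Protocol 9.3.1.5; SAP 6.8).

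**The concern.** Scheduled imaging should last as long as a patient can have an event in the analysis. Here it does not. Two treatments that leave a patient at risk for PFS and duration of response are missing from the list of treatments that leave scheduled scans in place.

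The main case is consolidative radiotherapy after the end-of-treatment (EOT) visit or after transplant. A site following 6.7 as written could stop scheduled CT while the analysis still counts the patient as progression-free. The trial is open-label and the tested PFS is per investigator, so a fixed scan schedule is an important safeguard on the timing of events.

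If radiotherapy is given mainly for residual disease, the patients who leave the schedule are not a random subset. Their number could also differ by arm if CR rates differ as assumed (35% and 60%). The documents do not say how radiotherapy would be chosen, so both are possibilities only.

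**Working it through.** **The plan's own figure.** The one power figure concerns CR at EOT: 35% v 60%, 50 per arm, two-sided alpha 0.1, about 80% power. With pooled variance under the null, z = (0.25 × √50 − 1.645 × √(2 × 0.475 × 0.525)) / √(0.35 × 0.65 + 0.60 × 0.40) = (1.768 − 1.162) / 0.684 = 0.887, which gives 81.2%. The figure reproduces. This point does not touch it, because 6.6 says "EOT evaluations must be performed before initiation of a new therapy, inclusive of radiotherapy and ASCT". No power is stated for PFS.

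**The two lists side by side.**

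| Treatment after study therapy | New anticancer therapy for PFS and duration? | Named as leaving scheduled scans in place? |
|---|---|---|
| ASCT | No | Yes |
| Consolidative radiotherapy | No | Not named |
| Mobilising chemotherapy | No | Not named |

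For the last two rows the treatment is not an event, and read literally no further scheduled scan is required. What follows depends on how a site applies the rule:
- In 6.7 the stop is written into the CT bullet only. If visits go on with history and physical examination, a responder can accrue progression-free time on examination alone (SAP 6.4).
- If the broader wording of 3.1 ends all follow-up assessments, the patient is censored at the last assessment without progression, unless an event is otherwise recorded.

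**Size (illustrative).** Inputs:
- Median PFS of 12 months, from the approximately 1 year reported in Protocol 1.1 for the large randomised comparison of salvage regimens. Exponential times are assumed.
- 50 patients per arm (Protocol 9.1).
- EOT at 9 weeks: 63 / 30.4375 = 2.07 months.
- Horizon of 24 months, the approximate minimum follow-up for the PFS analysis (Protocol 9.3.1.9).
- Radiotherapy near EOT in 5% to 20% of each arm. This is an assumption; the documents give no rate.

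Calculation:
- Events per arm by 24 months: 50 × (1 − 0.5^(24/12)) = 37.5.
- Chance of an event between EOT and 24 months, if event-free at EOT: 1 − 0.5^(21.93/12) = 0.718.
- 5% use: 2.5 × 0.718 = 1.8 events per arm.
- 10% use: 5 × 0.718 = 3.6, or 3.6 / 37.5 = about 10% of events.
- 20% use: 10 × 0.718 = 7.2.

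These are events that would occur after scheduled scans stop. They are not a count of events missed.

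**Upper bound on power.** Take 70 PFS events (70% of 100) and the hazard ratio that gives 80% power there: exp(−2 × (1.645 + 0.842) / √70) = 0.55. With power = Φ(√d × |ln HR| / 2 − 1.645), complete loss of 5%, 10% or 20% of events leaves d = 66.5, 63 or 56 and power of 78%, 76% or 72%. Real losses would be smaller, since many of these events are still captured.

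**The case against.** The best counter-argument is that 9.2.2.1 already says such patients have not started new anticancer therapy, so a careful site would read 6.7 the same way and keep scanning. That reading is available, but 6.7 neither cross-refers to Section 9 nor uses its list. If the Section 9 meaning already applied, ASCT would not need an exception of its own. Practice could therefore differ by site.

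Mobilising chemotherapy is the weaker case. Section 6.5 permits it, the Amendment 1 change log separates it from treatment of residual disease, and a transplant that follows restarts the visit schedule.

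Several stronger readings are tempting, but the documents do not support them:
- *These patients have no event and no further scans.* Sections 3.1 and 6.7 still call for CT when progression is suspected. Clinical progression, death and a later non-exempt therapy remain PFS events. The 6.7 PET bullet has no new-therapy stop, although the general rule in 3.1 is broader.
- *Section 6.6 proves that radiotherapy stops the scans.* Its list of new therapies also includes ASCT, after which scans plainly continue.
- *Section 6.7 contradicts itself on transplant.* The wording "initiation of a non-protocol therapy (with the exception of ASCT) for treatment of lymphoma" classifies why study treatment ended, while the CT bullet says when CT ends. The functions differ.
- *Follow-up after allogeneic transplant is undefined.* The conduct text exempts any stem cell transplant, so the SAP sensitivity analysis in which "Allogeneic SCT will not be regarded as an event" is already supported.
- *The SAP censors at the last scan before radiotherapy.* It censors at the last assessment without progression, and later physical examinations count.
- *The loss can be put at 4.7 v 2.9 events by arm.* That takes 20% of all non-CR patients (32.5 and 20, so 6.5 and 4) times 0.718. It includes patients already progressed at EOT, whose event has occurred. From Protocol 1.1, ORR 63% less CR 37% leaves 26% in PR, or 13 of 50; 20% of those is 2.6 control patients, with some stable disease to add.

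**Conclusion.** The mismatch is real and worth correcting. It reaches PFS and duration of CR, which are formally tested only if the CR test succeeds, and duration of objective response; it does not reach the primary endpoint. For consolidative radiotherapy, the literal conduct text removes required scheduled scans from patients whom the analysis keeps at risk, so progression may be dated late or missed.

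The likely size is modest and cannot be fixed from the documents: about 1.8 to 7.2 events per arm after scheduled scans stop, given 5% to 20% radiotherapy use, exponential PFS with a 12-month median, and sites following the literal rule. Only some of these would be lost. Informative or arm-dependent loss is plausible but not shown.

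**What to change.** Use one exception list in the synopsis, Section 3.1, the Figure 1 footnote and Section 6.7, for example:

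*Scheduled response assessments continue until disease progression, initiation of a new anticancer therapy, death, withdrawal of consent or study closure. Post-treatment consolidative radiotherapy, chemotherapy to mobilise PBSC, and stem cell transplant (autologous or allogeneic, whether or not the latter counts as a PFS event) are not new anticancer therapy for this purpose.*

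The clause on allogeneic transplant is needed. Section 9.2.2.1 exempts only ASCT, so a rule that simply stopped scans at a PFS event could end them after an allogeneic transplant, which the SAP sensitivity analysis needs to follow.

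The cost is amendment wording plus already scheduled scans in a few more patients, with no new visit or procedure type. Scans that were not done cannot be recovered at analysis.

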4.3.1 Discontinuation of Study Drug

A patient's treatment with study drug may be discontinued for any of the following reasons:

- Completed treatment
- Progressive disease
- Adverse event (AE)
- Investigator decision
- Patient decision, Non-AE
- Study termination by sponsor
- Other, Non-AE

Patients who discontinue from study treatment will remain on study for follow-up unless they withdraw consent.

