9.2.2.2 Overall Survival

Overall survival (OS) is defined as the time from date of randomization to date of death due to any cause. In the absence of confirmation of death, survival time will be censored at the last date the patient is known to be alive. If the last recorded date where a patient is known to be alive is the date of randomization, survival time will be censored on the date of randomization (i.e., OS duration of 1 day).

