9.3.1.7 Analysis Sets

Intent-to-Treat (ITT) Analysis Set: The ITT analysis set will include all randomized patients. Patients will be included in the treatment arm assigned at randomization regardless of the actual treatment received.

Modified Intent-to-Treat (mITT) Analysis Set: The mITT analysis set will include all patients who are randomized to the recommended dose level of 19A+RICE or RICE, and receive at least 1 cycle of study treatment. If the dose of denintuzumab mafodotin is modified from 3 mg/kg (e.g., to 2 mg/kg), the mITT Analysis Set includes all patients randomized

after the dose modification decision is made. Patients will be included in the treatment arm assigned at randomization regardless of the actual treatment received.

Safety Analysis Set: The safety analysis set will include all patients who receive any amount of denintuzumab mafodotin or any component of RICE. Treatment group will be determined using the actual treatment arm received, regardless of the randomization treatment assignment.

Per-Protocol (PP) Analysis Set: The per-protocol analysis set includes patients who receive at least 1 cycle of RICE (all components) or recommended dose of 19A+RICE (with all components of RICE) combination therapy and who had both a baseline and at least one post-baseline evaluable disease assessment (per the Lugano classification criteria or determination of clinical disease progression per the investigator), and no other major protocol deviations that could potentially affect tumor response. The per-protocol analysis set is a subset of the mITT analysis, and patients will be grouped in the same manner as mITT analysis set.

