7.5 Efficacy Analyses

The primary analysis CR rate will be based on the mITT analysis set. Secondary efficacy endpoint of response rate will also be summarized using the mITT analysis set. Secondary efficacy analysis of time to event endpoints will be summarized using the mITT analysis set. Additional analyses of efficacy endpoints using the ITT, safety, and per-protocol analysis sets will also be presented as appropriate. Analyses may also be performed using the subgroups listed in Section 6.8. For efficacy analyses, study day will be counted from date of randomization, i.e. Study Day = Date – Randomization Date + 1.

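### Protocol Section 6.7 limits scheduled survival follow-up to dosed patients, by a different criterion in each arm, in conflict with Section 3.1 and the synopsis, which leaves the supportive ITT analysis of OS incomplete

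*Protocol*

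**What the plan says.** Protocol Section 6.7 is the passage that sets out who is contacted for survival and when: patients "who receive at least one dose of denintuzumab mafodotin in the experimental arm or RICE in the control arm will be followed for survival", every 6 months after ASCT or EOT for 24 months and yearly after that. The next sentence reads "At the time of study closure, patients will be contacted for a final survival assessment" and does not say whether the dosing condition carries over.

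Other parts of the protocol set no dosing condition. Section 3.1 states: "Survival status follow-up will continue until patient death or study closure, whichever occurs first". The synopsis and the Figure 1 footnote say the same in substance. Section 4.3.1 adds: "Patients who discontinue from study treatment will remain on study for follow-up unless they withdraw consent". The opening of Section 6.7 has a similar rule for those who discontinue.

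On the analysis side, Protocol Section 9.2.2.2 states: "Overall survival (OS) is defined as the time from date of randomization to date of death due to any cause". A patient without a recorded death is censored when last known alive. If that date is the day of randomisation, "survival time will be censored on the date of randomization (i.e., OS duration of 1 day"). Comparing OS between arms is a secondary objective. For the analysis sets, Protocol Section 9.3.1.7 says "The ITT analysis set will include all randomized patients", while mITT requires at least 1 cycle of study treatment and groups patients by assigned arm. SAP Section 7.5 puts the main time-to-event analyses in mITT and continues: "Additional analyses of efficacy endpoints using the ITT, safety, and per-protocol analysis sets will also be presented as appropriate".

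**The concern.** OS is defined from randomisation, but the scheduled collection of survival data begins only once a patient has been dosed. Starting treatment is a post-randomisation event, and in an open-label trial it can depend on the arm, for example if a patient declines after learning the allocation. The supportive ITT analysis would show whether the mITT exclusions matter, and it needs vital status for exactly the patients whom the Section 6.7 sentence leaves out.

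The criterion also differs by arm. A control patient qualifies with one dose of RICE. A 19A+RICE patient with the same RICE exposure but no denintuzumab mafodotin does not. The protocol gives no reason for the difference. Vital status that is not collected during the trial may not be recoverable later.

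**Working it through.** There is no plan figure to reproduce for OS: no power, event target or formal test is stated. The only design figure is about 80% power for CR (35% against 60%, about 50 per arm, two-sided alpha 0.10). It reproduces at 81.2% by the pooled normal formula and 79.9% by exact enumeration, and it has no bearing on this point. The check is therefore a comparison of passages followed by a bounding calculation.

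**1. Who falls outside the Section 6.7 sentence**

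| Patient | Survival sentence in 6.7 | Main OS set (mITT) | ITT |
|---|---|---|---|
| Control, never dosed | Outside | Out | In |
| 19A+RICE, never dosed | Outside | Out | In |
| Control, at least 1 cycle of RICE | Inside | In | In |
| 19A+RICE, at least 1 cycle of RICE, no denintuzumab mafodotin | Outside | Can be in | In |
| 19A+RICE, at least 1 cycle of both | Inside | In | In |

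The first two rows affect only the ITT analysis. The fourth can reach the main analysis, because mITT keeps patients in the assigned arm whatever they received. It should be rare, since denintuzumab mafodotin is given before rituximab on Day 1 (Protocol Sections 5.2.2 and 5.3.3). Such a patient has also started study treatment, so the general rule for those who discontinue may still cover them.

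**2. Whether another rule covers the never-dosed patient**

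The rules for patients who discontinue treatment do not plainly reach someone who never started. The survival schedule counts from ASCT or EOT. If there is no EOT visit, SAP Section 6.4 takes the earlier of the end-of-study date and 30 days after the last dose, and a never-dosed patient has no last dose. Section 3.1 does cover such a patient, but it gives no schedule. The two sections therefore conflict, and a site could reasonably apply the more detailed one.

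**3. Size**

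Inputs: about 50 patients per arm (Protocol Section 9.1); 3-year OS of 50%, from the randomised comparison of salvage regimens cited in Protocol Section 1.1, used for illustration only; and k patients in an arm with unknown vital status. The documents give no value for k, so 1 to 5 is an assumption.

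If OS among the 50 − k followed patients is 50%, the rate for the whole arm lies between

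- lower bound (all k died): 0.5 × (50 − k) / 50
- upper bound (all k alive): [0.5 × (50 − k) + k] / 50

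| k | Lower | Upper | Width (k/50) |
|---|---|---|---|
| 1 | 24.5/50 = 49% | 25.5/50 = 51% | 2 points |
| 2 | 24/50 = 48% | 26/50 = 52% | 4 points |
| 3 | 23.5/50 = 47% | 26.5/50 = 53% | 6 points |
| 5 | 22.5/50 = 45% | 27.5/50 = 55% | 10 points |

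The width is k/50 whatever the survival rate. With k unknown in one arm and full follow-up at 50% in the other, the difference between arms is uncertain by ±1 point (k = 1) to ±5 points (k = 5).

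**The case against.** Most of the case on the other side stands.

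- The main OS analysis is mITT, so never-dosed patients are outside it whatever Section 6.7 says. The ITT analysis is additional: the SAP presents it as appropriate, and Protocol Section 9.3.5 says only that it may be done.
- OS has no formal test. The tested endpoints are CR, PFS and duration of CR.
- Randomisation falls within 1 business day of the planned first dose (Protocol Section 5.1), which leaves little time for patients to drop out undosed.
- Some patients who leave on learning their allocation will withdraw consent, and no rewording recovers their data.

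A reader might infer that OS cannot be compared for all randomised patients. The documents do not support that. Survival follow-up is unconditional in Section 3.1, the synopsis and the Figure 1 footnote, and an ITT curve can be computed with censoring. The problem is incomplete data and possible bias.

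A reader might also infer that every never-dosed patient is censored at 1 day and that their deaths are never collected. That goes too far. Censoring is at the last date known alive, and 1 day applies only when that is the day of randomisation. Death is a listed reason for leaving the study (Section 4.3.2), and the date and reason are recorded (Section 6.8), so a death before dosing can be captured while the patient is still on study.

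What these arguments leave standing is the conflict between sections, the unexplained arm-specific criterion, and the absence of a survival schedule for never-dosed patients.

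**Conclusion.** The point holds as a low-cost improvement to the protocol. Section 6.7 conflicts with Section 3.1, the synopsis and the Figure 1 footnote on who is followed for survival, and its criterion differs between arms. Applied as written, it would leave the supportive ITT analysis of OS incomplete, with never-dosed patients censored early and possibly informatively. The main mITT analysis is largely unaffected, apart from the rare 19A+RICE patient who receives RICE alone. No design figure changes.

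The size is unknown and probably small. The bounds of 49–51% to 45–55% rest on an assumed 1 to 5 patients of unknown status in an arm of 50 and on the cited 50% 3-year OS. The planned OS analysis comes about 2 years after the last enrolment, or earlier if 70% of patients have had an event, so the 3-year rate only sets the scale. It may be tempting to assume that undosed patients would be mostly controls; nothing in the documents supports that or any particular undosed share.

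**What to change.** Reword the survival sentence in Protocol Section 6.7 along these lines: all randomised patients, whether or not they received any study treatment, are followed for survival at 6-month intervals for the first 24 months and yearly after that, until death or study closure, unless consent to follow-up is withdrawn; the schedule runs from ASCT or EOT, or from randomisation if there is no EOT visit. State that the contact at study closure covers the same patients. This removes the arm-specific criterion and brings Section 6.7 into line with Section 3.1, the synopsis and the Figure 1 footnote.

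The cost is one amended sentence and a few extra survival contacts, with no new procedures. Data from patients who withdraw consent would still be missing, so the number with unknown vital status should be reported by arm beside any ITT analysis of OS.
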